6.2 Secondary outcome

The number of patients with increased tracer-uptake over the pancreatic lesion with and without TOF, and thus the better demarcation of pancreatic lesions of the adjacent anatomical structures will be compared using the McNemar test. Also, differences between the SUVmax values with and without TOF will be compared using the t-test. Furthermore, the mean tumor size including the standard deviation will be calculated.

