Protocol

Evaluation of the diagnostic value of TOF-18F-FDG PET/CT in patients with suspected pancreatic cancer

September 2013

Content

Summary.....	2
Background information.....	4
Study hypothesis.....	6
Aim of the study.....	6
Study process.....	7
Patients.....	8
Patient recruitment.....	8
Protocol: PET/CT.....	9
Data handling.....	10
References.....	11

Summary

According to the application for the responsible ethics committee of the Medical University of Graz a study is to be performed for the „*evaluation of the diagnostic value of TOF-18F-FDG PET/CT in patients with suspected pancreatic cancer*“.

The essential idea of the study is the analysis of the use of early (30min p.i.) and delayed (90min p.i.) imaging as well as a diagnostic CT of the abdomen with contrast medium and pancreas protocol for characterization of pancreatic masses with TOF (Time-of-Flight)-18F-FDG-PET/CT.

According to current scientific evidence, there are no studies in the literature regarding the characterization of pancreatic masses by the "Time-of-Flight"-technique (TOF) within PET/CT. Usually, the differentiation between chronic pancreatitis and pancreatic carcinoma is often not possible. Likewise, the differentiation of the pancreas from surrounding anatomical structures (duodenum) in PET/CT with low dose CT is often not possible. An exact diagnosis of a possible malignancy or benignancy, as well as the precise anatomical localization of the detected lesion, is however of decisive importance for the further therapeutic procedure [1-4]. If a benign lesion is present, an extensive operation (Whipple operation) may not be necessary.

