As a rule, patients with suspected pancreatic cancer are assigned to the Division of Nuclear Medicine for 18F-FDG PET-CT imaging. Early (30min p.i.) and delayed images (90min p.i.) are taken to better distinguish between malignant from inflammatory lesions. After the PET/CT examination, a TOF-reconstruction is performed, which does not require the presence of the patient, but improves the image quality to differentiate the lesion in the pancreas better. For better anatomical demarcation of the pancreas of adjacent structures (duodenum) additionally a diagnostic CT of the abdomen (up to the iliac crest) with pancreas protocol (2 phases) with i.v. administration of iodine-containing contrast medium (Visipaque®) and oral administration of a negative contrast medium (500 ml water) for intestinal distension is additionally performed. After consultation with the referring physician, it must be ensured for reasons of radiation hygiene that the patients do not have a diagnostic CT with contrast agent before the PET/CT examination. If this is not possible, a diagnostic CT of the upper abdomen (up to the lower liver margin) is performed with pancreas protocol with 2 phases (arterial and portal venous). In most cases these patients are operated, only in the rarest of cases, a biopsy/brush swab is carried out beforehand. The histopathological preparation of the surgical specimen is then performed. These steps are routine. This approach is to be retained in the project. These steps are

- 1) Assignment of the patient to the TOF-PET-CT (with images 30min und 90min p.i.)
- 2) Performing a diagnostic CT of the abdomen with parenteral and oral contrast media and pancreas protocol as part of the PET/CT examination
- 3) Routine performance of the operation/fine needle puncture
- 4) Routine histopathological evaluation

With the help of the enclosed Informed Consent, the patient's information and written consent are duly given. Furthermore, in the case of administration of parenteral contrast medium, the relevant information is routinely provided using a contrast medium information sheet.

The administration of parenteral contrast media is performed according to the ESUR Guidelines [1].

Background information

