The 18F-FDG PET/CT is indicated for staging in patients with suspected pancreatic carcinoma and was also classified as 1a indication for differentiation between inflammation and pancreatic carcinoma according to the 3rd German Interdisciplinary Consensus [6]. In patients with suspected pancreatic carcinoma, diagnosis is often only possible with difficulty due to the limited anatomical assignment of small focal lesions and discreetly increased tracer-uptake, differentiation between benign and malignant is often not possible, i.e., differentiation between chronic pancreatitis and a malignant process is often only possible to a minimal extent. According to clinical studies [7;8;21-26], the TOF-technique and additional i.v. administration of iodine-containing contrast medium and oral administration of a negative contrast medium can significantly improve the sensitivity and anatomical differentiation of the target organ from adjacent structures. However, this technique has not yet been used in patients with suspected pancreatic cancer.

Another already established method to better distinguish inflammatory from malignant lesions in PET/CT is to take images at two different time points and to compare the Standard Uptake Value (SUV), a measure of regional accumulation intensity, at these two times [3;17;18]. Here an increased FDG-uptake already in the early images is classified as benign/inflammatory, and an increase in FDG -

uptake in the delayed images is classified as malignant. A missing FDG uptake both in the early and the delayed images is considered benign.

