2.1 Sample size planning

One hundred eighteen patients would be required to demonstrate an improvement in specificity of 25% (to 70%) with the new method assuming a specificity of the current method of 45% at a prevalence of malignant lesions of 70% (corresponding to 30% benign lesions). The calculation of these values is based on a formula that selects the sample size so that the lower limit of the 95% confidence interval by the expected specificity of the new method most probably exceeds the specificity value of the current method, i.e., the confidence interval no longer contains this value. With a power of (in this case) 90%, you can say that the specificity of the new method is higher than the old one.

3. Aims and objectives

The aim of the study is to analyze if 30 and 90min p.i. images and a diagnostic CT of the abdomen in the context of TOF-18F-FDG-PET/CT can improve the differentiation between malignant and benign lesions in the pancreas in patients with suspected pancreatic cancer.

4. Outcomes

This section will present the outcomes investigated to answer the study aims and objects. The analyses are described in section 6 Analyses.

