4.2 Secondary outcome

Better demarcation of pancreatic lesions of the adjacent anatomical structures as well as the tumor size in cm.

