4.3 Safety outcomes

Adverse events

Possible adverse events are reported in the case report form.

Concomitant medications

Usage of diabetes or thyroid medications before PET/CT examination will be recorded.

5. Populations to be analyzed

There is only one population in this clinical trial. All patients undergo a TOF-18F-FDG PET/CT examination with images 30 and 90min p.i. with a diagnostic CT of the abdomen. In all patients exist PET images with and without TOF.

6. Analyses

All outcomes will be presented using ROC-analysis or descriptive statistics. SPSS version 25 and R will be used for all statistical analysis.

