6.1 Primary outcome

The primary analysis will compare the SUVmax values of all detected pancreatic lesions in the PET/CT images 30 and 90min p.i. with and without TOF using ROC-analysis. AUC values with and without TOF 30 and 90min p.i. will be compared using the DeLong-test. Sensitivity and specificity of SUVmax of each imaging modality (with and without TOF) in correlation with the

histopathological results will be calculated. Furthermore, a cut-off value of SUVmax for differentiating malignant and benign pancreatic lesions will be computed using ROC-analysis. Besides, sensitivity, specificity, diagnostic accuracy and the positive and negative predictive value of the results of the PET/CT findings in correlation with the histopathological results will be calculated.

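### SAP 6.2 reports a with/without-TOF count of uptake-positive patients as better demarcation, but the count measures lesion visibility, not borders

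*SAP*

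**What the plan says.** SAP 4.2 gives the secondary outcome as "Better demarcation of pancreatic lesions of the adjacent anatomical structures as well as the tumor size in cm". It supplies no scale, reader or criterion for demarcation.

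The only analysis offered for the demarcation part is the first sentence of SAP 6.2, which compares "The number of patients with increased tracer-uptake over the pancreatic lesion with and without TOF, and thus the better demarcation of pancreatic lesions" between reconstructions with the McNemar test. The comparison is paired, because SAP section 5 states: "In all patients exist PET images with and without TOF".

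The rest of 6.2 compares SUVmax with and without TOF by a t-test and gives the mean and standard deviation of tumor size.

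The protocol mentions demarcation or delineation in several places:

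- The Summary notes that "the differentiation of the pancreas from surrounding anatomical structures (duodenum) in PET/CT with low dose CT is often not possible", and adds a contrast-enhanced scan: "For better anatomical demarcation of the pancreas of adjacent structures (duodenum) additionally a diagnostic CT of the abdomen".
- The Summary also says that TOF reconstruction improves image quality so that the lesion can be differentiated better.
- Background information says that TOF together with contrast media "can significantly improve the sensitivity and anatomical differentiation of the target organ from adjacent structures".
- Background information also says that SUV serves both staging and the determination of tumor boundaries.

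**The concern.** Increased uptake is a statement about presence: the lesion stands out or it does not. Demarcation is a statement about an edge: the lesion can be told apart from what lies next to it, or it cannot. SAP 6.2 moves from the first to the second with the words 'and thus', and nothing in either document supplies the missing step.

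Followed as written, the plan could err in two ways. It could report that TOF improves demarcation when only visibility changed. It could also report no improvement when edges did become clearer in lesions already visible on both reconstructions. Either statement would appear in the results under the name of a pre-specified secondary outcome.

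**Working it through.** **1. The plan's own figure.** The only design figure stated is N = 118 (SAP 2.1). Its inputs are specificity 45% for the current method and 70% for the new one, a 95% confidence interval, 90% power, and the benign share given "at a prevalence of malignant lesions of 70% (corresponding to 30% benign lesions").

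- Benign patients: (1.960 + 1.282)² × 0.70 × 0.30 / 0.25² = 35.30
- Total: 35.30 / 0.30 = 117.7, rounded up to 118

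The figure reproduces. It concerns specificity and does not depend on the analysis in 6.2.

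**2. What the count can register.** Let b be the number of patients uptake-positive only with TOF, and c the number positive only without TOF. McNemar's test uses b and c alone.

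| Uptake without TOF / with TOF | Possible change at the border | Contribution to the test |
|---|---|---|
| positive / positive | much clearer, unchanged or worse | none |
| negative / negative | not reflected in the count | none |
| negative / positive | may or may not be separable from neighbours | counts for TOF |
| positive / negative | may or may not be separable from neighbours | counts against TOF |

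In no row does the entry depend on the border.

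**3. Is a border measure derived elsewhere?** No. SAP 4.2 names the outcome without a criterion. The protocol says SUV is used for tumor boundaries, but 6.2 derives no boundary from it: SUVmax is a single peak value with no spatial extent. Tumor size is summarised once, with no comparison between reconstructions.

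**4. Illustration with assumed counts.** The documents give no discordant counts, so b and c are assumptions. SAP 6.2 does not state the version of the test, its alpha or its sidedness; two-sided tests are used here.

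Exact p = 2 × P(Bin(b + c, 0.5) ≤ min(b, c)), capped at 1:

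- 5 v 0: 2 × 0.5⁵ = 0.063
- 6 v 0: 2 × 0.5⁶ = 0.031
- 7 v 0: 2 × 0.5⁷ = 0.016

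Other versions for 6 v 0:

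- uncorrected: 6² / 6 = 6.0, p = 0.014
- continuity-corrected: (6 − 1)² / 6 = 4.17, p = 0.041

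Paired difference for 6 v 0: 6/118 = 5.1 points. For the Bonett-Price interval, add 1 to each discordant cell and 2 to n:

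- proportions: 7/120 = 0.0583 and 1/120 = 0.0083; difference 0.0500
- standard error: √[(0.0583 + 0.0083 − 0.0500²) / 120] = 0.0231
- 95% CI: 0.0500 ± 1.96 × 0.0231, or 0.5 to 9.5 points

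The other 112 patients (112/118 = 95%) add nothing to the test, whatever happens to their lesion borders.

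**5. The opposite extreme.** Suppose TOF sharpened the border in all 118 patients but changed no patient's uptake status. Then b = c = 0 and the exact p is 1. The same interval is 0 ± 1.96 × √[(1/120 + 1/120) / 120] = ±2.3 points. Under the present wording, this would be reported as no demarcation benefit, and with apparent precision.

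**The case against.** The strongest reply is that the documents give reasons to connect TOF and uptake with delineation. The protocol Summary credits TOF reconstruction with better differentiation of the lesion. Background information credits TOF and contrast media jointly with better anatomical differentiation, and treats SUV as a tool for tumor boundaries. On this view, 'and thus' is an operational definition: uptake positivity stands in for demarcation.

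Part of that stands. The link is plausible, and the count may be related to demarcation. But Background information names sensitivity and anatomical differentiation as two separate gains, and a count of positive patients speaks to the first. Nothing in the documents validates it as a stand-in for the second.

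It is also fair to say that the figures above rest on invented counts and that 0 v 0 is a constructed extreme. They show how the test behaves; they do not predict the trial's result. The defect is conceptual and would remain without them.

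A reader might draw three stronger inferences, which the documents do not support:

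- **That demarcation belongs to the diagnostic CT, so a TOF comparison is misdirected.** The Summary statements on CT concern the pancreas as an organ and the duodenum, whereas SAP 4.2 and 6.2 concern lesions. The protocol also credits TOF with differentiating the lesion.
- **That 6.2 is faulty because it cannot isolate the effect of the CT.** It does not claim to. Nor do the documents describe one uniform contrast CT: the scan range varies with earlier imaging, and contrast medium is withheld at certain laboratory values.
- **That 6.2 fails to show a diagnostic gain.** It claims none. That question belongs to SAP 6.1, where "AUC values with and without TOF 30 and 90min p.i. will be compared using the DeLong-test" and results are set against histology.

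**Conclusion.** The point holds in a limited form. The uptake count is a valid paired comparison of lesion visibility with and without TOF. As evidence on demarcation it is at most an unvalidated surrogate, and it cannot by itself carry a demarcation conclusion. This follows from what the variable records and from the absence of any border measure in either document; it does not depend on the assumed counts.

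The reach is the demarcation part of one secondary outcome. Tumor size keeps its own descriptive summary, and the ROC analyses in SAP 6.1 and N = 118 are unaffected. On the assumed counts, six one-sided discordant patients of 118 would suffice for a nominally significant demarcation claim at two-sided 0.05 (exact p = 0.031), while five would not (p = 0.063). How many will occur cannot be judged from the documents. The wording should be corrected before the analysis.

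To say that the count has nothing to do with demarcation would go too far, given the protocol's statements on TOF and SUV.

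**What to change.** In the first sentence of SAP 6.2:

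1. Strike the clause that begins 'and thus' and equates the count with demarcation.
2. Name the analysis lesion detectability (uptake positivity) with and without TOF.
3. Keep the McNemar test and report the paired difference with a 95% CI beside it.
4. Add that no conclusion on demarcation will be drawn from this count.
5. State that the demarcation part of SAP 4.2 will be reported as not assessed, unless a border criterion is written into the SAP before the analysis, to be read on the existing images blinded to histology and to reconstruction. The criterion must be fixed in advance; a general reference to border assessment would leave room for a choice after the results are known.

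The t-test and tumor size sentences can stay.

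The minimum change is wording only, in a SAP still marked Draft 0.1, and needs no new patients or scans. The downside is that the demarcation outcome may carry no formal result. If the sponsor wants one, the border reading covers 118 × 2 = 236 image sets per reader per time point.

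SAP 6.2 also does not say what counts as increased uptake or which time point is used. These are separate gaps, but the same edit is a convenient place to close them.
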